7.2.2 Blood Specimens for Circulating Nucleic Acid (CNA) Profiling

Collection of peripheral plasma samples optimized for nucleic acid analysis (e.g., circulating free DNA [ctDNA] or RNA [ctRNA]) will be mandatory for all patients at baseline, week 8. Markers that may be analyzed include, but may not be limited to ALK rearrangement, and ALK kinase domain mutations.

7.3 Safety Assessments

The following parameters will be assessed at time points detailed in **Table 1** Schedule of Activities:

- ECG;
- Safety laboratory data;
- ECOG PS (ref to **Appendix 1** is needed);
- Vital signs;
- AEs.

7.3.1 12 Lead ECG

A 12-Lead ECG will be performed at screening and baseline with a 10 second rhythm strip. If the subject experiences signs or symptoms of a cardiac or neurologic disorder (specifically syncope, dizziness, seizures, or stroke), ECG should be obtained at the time of the event.

To ensure safety, if there is finding of QTc >500 msec, the ECG must be repeated. If there is finding of QTc >500 msec again (i.e., \geq CTCAE Grade 3), the ECG must be reviewed by qualified personnel at the site as soon as the finding is made, including verifying that the machine reading is accurate and that the Fridericia's or Bazett's correction formula is applied.

An electronic reading of prolonged QTc must be confirmed by a manual reading. Before concluding that an episode of QTc prolongation is due to study drug, thorough consideration should be given to potential precipitating factors (e.g., a change in the subject's clinical condition, the effect of concurrent medication, electrolyte disturbance) and a possible evaluation by a specialist. If the QTc reverts to \leq 500 msec, and it is the opinion of the investigator that the prolongation was not due to the study drug, treatment may be continued with regular ECG monitoring.

7.3.2 Safety Laboratory Data

Safety laboratory studies may be done up to 72 hours prior to the point indicated on the Schedule of Activities (Table 1) on any cycle, to facilitate availability of results to the investigator at the time of the clinic visit.

Table 5: Laboratory Evaluations

Screening for Eligibility		
Hematology	Blood Chemistry	Other
Hemoglobin	AST (SGOT)	Urinalysis (blood, protein, glucose, by dipstick; microscopic examination of sediment if abnormalities on urine dipstick) Calculation of the creatinine clearance determined by the Cockcroft-Gault formula or site's standard formula. Pregnancy Test (urine or serum)
Platelet count	ALT (SGPT)	
WBC count	Creatinine	
Absolute neutrophil count	Total bilirubin	
Absolute lymphocyte count		
Absolute monocyte count		
Baseline and during the Treatment Period		
Hematology	Blood Chemistry	Other
Hemoglobin	Alkaline phosphatase	Pregnancy test (urine or serum) at baseline. In case of serum sample, pregnancy test needs to be conducted within 72 hours prior to Day 1 of the first 8 weeks. In case of urine sample, pregnancy test needs to be conducted on Day 1 of the first 8 weeks before study treatment is started. Pregnancy test (urine or serum) at end of treatment if mandated by institutional policy or at the discretion of the investigator.
Platelet count	AST, ALT	
WBC count	Total bilirubin	
Absolute neutrophil count	Calcium (total or ionized)	
Absolute lymphocyte count	Magnesium	
Absolute monocyte count	Potassium	
	Sodium	
	BUN or urea	
	Albumin	

7.3.3 Vital Signs

Vital signs include pulse rate, sitting or supine blood pressure, respiratory rate and body temperature.

The information will be recorded in the subject's medical records and if clinically significant, data will be recorded as an AE in the CRF.

8. ADVERS'E EVENT REPORTING

All observed or volunteered AEs regardless of treatment group or suspected causal relationship to the investigational product(s) will be reported as described in the following sections.

For all AEs, the investigator must pursue and obtain adequate information both to determine the outcome of the AE and to assess whether it meets the criteria for classification as a SAE requiring immediate notification to the Sponsor or its designated representative. For all AEs, sufficient information should be obtained by the investigator to determine the causality of the AE. The investigator is required to assess causality. Follow-up by the investigator may be required until the event or its sequelae resolve or stabilize at a level acceptable to the investigator, and the Sponsor concurs with that assessment.

As part of ongoing safety reviews conducted by the Sponsor any non-serious AE that is determined by the Sponsor to be serious will be reported by the Sponsor as an SAE. To assist in the determination of case seriousness further information may be requested from the investigator to provide clarity and understanding of the event in the context of the clinical study.

8.1 Reporting Period

For SAEs, the active reporting period to the Sponsor or its designated representative begins from the time that the subject provides informed consent, which is obtained prior to the subject's participation in the study, i.e., prior to undergoing any study-related procedures and/or receiving investigational product, through and including 28 calendar days after the last administration of the investigational product regardless of the start of any subsequent cancer therapy. SAE should be reported via the CRF in the active reporting period. Following the active safety reporting period, other SAEs of which the investigator becomes aware should be reported to Pfizer, unless the SAE is attributed by the investigator to complications of either the underlying malignancy or any subsequent anti-cancer therapy or to the patient's participation in a subsequent clinical study.

Non-serious adverse events should be recorded on the CRF from the time the subject has taken at least one dose of study treatment through last subject visit.

If a subject begins a new anticancer therapy, the AE reporting period for non-serious AEs ends at the time the new treatment is started.

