lorlatinib enrolled in this study, follow-up visits are performed by investigator to collect study-related data, including data on effectiveness, tumor status, and other study required variables. A final data collection will be performed at death, withdrawal of consent, loss to follow-up, or the end of the study which is the earliest occurrence. There is no fixed visit schedule; visits will follow local routine clinical practice. Data will be collected until the 60th month after patient enrolled in this study (last follow-up time) or the death of patients due to any cause, loss to follow-up or withdrawal from the study which is the earliest occurrence.

Data type:

The clinical data collected for this study include, but is not limited to:

Collect patients' baseline demographic information (including age at diagnosis, gender, height, weight, physical examination, smoking status), ECOG score, past history, baseline disease characteristics (disease stage, molecular typing, pathological diagnosis), laboratory test results (blood routine, urine routine, blood biochemistry, coagulation function tests, electrocardiogram, echocardiography, vital signs), ALK genetic testing methods and results, test specimen types, imaging tests (tumor assessment[size, number, and location], medication treatment, adverse events, post-resistance gene testing, dose modification regimens, reasons for lorlatinib dose modification, interruption or discontinuation, PRO (if data is available in clinical practice) and survival status.

Collection and recording of SAEs and AEs will commence once the study participant has provided informed consent and terminate till 28 (and no more than 35) days after administration of the last dose of lorlatinib. After this period, only lorlatinib-related SAEs must be reported to the Pfizer. SAEs should be monitored until they are resolved or are clearly determined to be due to a patient's stable or chronic condition or intercurrent illness(es). All patients will be periodically contacted for survival and safety information unless the patient requests to be withdrawn from the study. Survival status is also encouraged to be confirmed through a telephone follow-up by the investigator or designee at the end of the study or withdrawal from the study.

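### Protocol sections 3.1 and 8.1 give different start and end points for recording non-serious AEs and different rules for SAEs after the reporting window

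*Protocol*

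**What the plan says.** Protocol section 3.1, under its data-type text, treats serious and non-serious events together. It states: "Collection and recording of SAEs and AEs will commence once the study participant has provided informed consent". Collection is to "terminate till 28 (and no more than 35) days after administration of the last dose of lorlatinib", with no earlier stop if new anticancer therapy begins. It then adds: "After this period, only lorlatinib-related SAEs must be reported to the Pfizer".

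Protocol section 8.1 separates the two kinds of event. SAE reporting "begins from the time that the subject provides informed consent" and runs "through and including 28 calendar days after the last administration of the investigational product regardless of the start of any subsequent cancer therapy". Non-serious AEs are recorded "from the time the subject has taken at least one dose of study treatment through last subject visit", and that period closes when a new anticancer therapy starts. After the SAE window, "other SAEs of which the investigator becomes aware should be reported to Pfizer, unless the SAE is attributed by the investigator to complications" of the malignancy or of later anticancer therapy, or to taking part in a later study.

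No definition of the last subject visit is given. Section 9.3 bases safety summaries on all dosed subjects and states no event window that would settle the difference.

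**The concern.** A site that follows 3.1 and a site that follows 8.1 will not record the same non-serious AEs or report the same late SAEs. Section 3.1 plans about 8 sites and no fixed visit schedule, so different readings across sites are a practical risk.

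Safety and tolerability of the treatment mode is a secondary objective (section 2.1), AEs are a listed endpoint (section 2.2), and section 3.2 covers the safety of lorlatinib together with local therapy. If windows differ by site, AE percentages pool patients observed for different lengths of time. A late SAE that an investigator ascribes to local therapy and not to lorlatinib is the kind of event on which the two late-SAE rules part. Local therapy is given while lorlatinib continues, so it is not plainly a subsequent therapy under the 8.1 exceptions. Section 3.1 also has patients contacted periodically for survival and safety information, so investigators may well learn of such events.

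A statistical analysis plan can restrict which recorded events are tabulated. It cannot recover events that a site was told not to record.

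**Working it through.** The plan states no figure to reproduce. The check sets the two sections side by side and counts days.

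| Item | Section 3.1 | Section 8.1 | Difference |
|---|---|---|---|
| Start, SAEs | consent | consent | none |
| End, active SAE window | 28 to 35 days after last dose | 28 days after last dose | 28 − 28 = 0 to 35 − 28 = 7 days |
| Start, non-serious AEs | consent | first dose | up to 28 days |
| End, non-serious AEs | 28 to 35 days after last dose | last subject visit, or new anticancer therapy if earlier | see below |
| SAEs after the window | lorlatinib-related only | all the investigator becomes aware of, less three attributed causes | see below |

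**Start of non-serious AEs.** Section 7.1 allows consent up to 28 days before treatment, so the two starts can be up to 28 days apart. The visit procedures fit 8.1: section 6.1 collects SAE data at baseline, and AE data first appear on Day 1 (section 6.2.1).

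**End of non-serious AEs, no new therapy.** Inputs: lorlatinib stops at month 24 (assumed for illustration); follow-up lasts at most 60 months from first dose (section 6.2.8); the post-treatment visit falls 28 to 35 days after discontinuation (section 6.2.7).
- Section 3.1 ends at about month 24 + 1 = 25.
- Section 8.1, if the last subject visit is the post-treatment visit: also about month 25. Gap about 0.
- Section 8.1, if the last subject visit is at month 60: gap 60 − 25 = 35 months.

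**End of non-serious AEs, early new therapy.** Assume new therapy starts 7 days after the last dose. Section 8.1 stops at day 7 and section 3.1 at day 28 to 35, so 8.1 is shorter by 28 − 7 = 21 to 35 − 7 = 28 days. The conflict therefore runs in both directions.

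**Late SAEs.** Take an SAE after the window that is judged unrelated to lorlatinib and is not attributed to the malignancy, later anticancer therapy or a later study. Section 8.1 asks for it; section 3.1 does not.

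**Window common to both sections, non-serious AEs.** The later start is first dose. The earlier end is 28 days after the last dose, or the start of new anticancer therapy if that comes first. In the 7-day example the common window closes at day 7, not day 28.

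**The case against.** The best defence is that section 8 governs. Its opening text says AEs are reported as the sections that follow describe, and the baseline and Day 1 procedures match 8.1 on the start date. On that view the paragraph in 3.1 is stray text. This makes 8.1 the more likely working rule for the start, but it does not cancel the explicit limit to lorlatinib-related SAEs in 3.1. That paragraph is current protocol text which a site may follow.

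On the end date, the last visit in section 6 that routinely lists AE review is the 28-to-35-day post-treatment visit, and section 6.2.8 then covers progression, later therapies and survival. If that visit is what 8.1 means, the end dates almost coincide when no new therapy starts. This stands as one reading. The periodic safety contact in 3.1 leaves the longer reading open, so a range has to be given. The long end also needs a patient to spend three years off lorlatinib without new therapy.

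On late SAEs, 3.1 uses 'must' and 8.1 uses 'should', so one might be a minimum and the other a request. The word 'only' in 3.1 makes that strained. It is fair that few local-therapy events are exposed: lorlatinib continues after local therapy, so the rules diverge only for events later than 28 to 35 days after the last dose.

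Pre-dose non-serious events may also never be counted as treatment-emergent, and that definition belongs to the analysis plan. This limits the effect of the start-date conflict on reported incidence. It does not remove the conflict over what is to be recorded.

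**Conclusion.** The two sections contradict each other on three points: when non-serious AE recording starts, when it ends, and which SAEs are reportable after the window. The starts differ by up to 28 days. The ends differ by about 0 to about 35 months for a patient who stops at month 24 without new therapy, and by 21 to 28 days the other way if new therapy starts 7 days after the last dose. The month-24 stop and the 7-day switch are illustrations, not figures from the plan.

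A reader might infer more than the text supports:
- *That SAE collection as a whole is in conflict.* It is not. The active SAE windows share a start and end within 7 days of each other; only the rule after the window differs.
- *That 35 months is the size of the discrepancy.* It is the upper end for that example, and holds only if the undefined last visit falls at month 60.
- *That different starts for SAEs and non-serious AEs are an error.* The split in 8.1 is a legitimate choice; the fault is that 3.1 does not share it.

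The primary endpoint is untouched. What is exposed is the consistency of AE counts and of late-SAE capture across sites. The documents do not show which late-SAE rule or end date is intended.

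**What to change.** Reconcile the data-type paragraph of section 3.1 with section 8.1 so that both carry:
- the same start and the same end for non-serious AEs, including whether new anticancer therapy closes the period;
- the same end of the active SAE window, either with or without the allowance to 35 days;
- one rule for SAEs after that window.

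SAEs and non-serious AEs may keep different starts, provided both sections say so. Define 'last subject visit' by naming the visit in section 6 that it refers to.

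If AE incidence is tabulated on the window common to both sections, then for non-serious AEs that window is first dose to 28 days after the last dose or the start of new anticancer therapy, whichever is earlier.

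The cost is protocol wording and matching CRF guidance. No new visits or data sources are needed.

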8.2 Definition of an Adverse Event

An AE is any untoward medical occurrence in a clinical investigation during which a subject is administered a product or medical device; the event need not necessarily have a causal relationship with the treatment or usage. Examples of AEs include but are not limited to:

- Abnormal test findings;
- Clinically significant symptoms and signs;
- Changes in physical examination findings;
- Hypersensitivity;
- Drug abuse;
- Drug dependency.

Additionally, they may include the signs or symptoms resulting from:

- Drug overdose;
- Drug withdrawal;
- Drug misuse;
- Drug interactions;
- Exposure during pregnancy;
- Exposure via breast-feeding;
- Medication error.

Worsening of signs and symptoms of the malignancy under study should be reported as AEs in the appropriate section of the CRF. Disease progression assessed by measurement of malignant lesions on radiographs or other methods should not be reported as an AE.

8.3 Abnormal Test Findings

The criteria for determining whether an abnormal objective test finding should be reported as an AE are as follows:

- Test result is associated with accompanying symptoms, and/or
- Test result requires additional diagnostic testing or medical/surgical intervention, and/or
- Test result leads to a change in study dosing or discontinuation from the study, significant additional concomitant drug treatment, or other therapy, and/or
- Test result is considered an AE by the investigator.

Merely repeating an abnormal test, in the absence of any of the above conditions, does not constitute an AE. Any abnormal test result that is determined to be an error does not require reporting as an AE.

8.4 Serious Adverse Events

A SAE is any untoward medical occurrence at any dose that:

- Results in death;
- Is life-threatening (immediate risk of death);
- Requires inpatient hospitalization or prolongation of existing hospitalization;
- Results in persistent or significant disability/incapacity (substantial disruption of the ability to conduct normal life functions);
- Results in congenital anomaly/birth defect.

Progression of the malignancy under study (including signs and symptoms of progression) should not be reported as a SAE unless the outcome is fatal within the safety-reporting period. Hospitalization due to signs and symptoms of disease progression should not be reported as a SAE. If the malignancy has a fatal outcome during the study or within the safety-reporting period, then the event leading to death must be recorded as an AE and as a SAE with CTCAE Grade 5 (see Section 8.6).

Medical and scientific judgment is exercised in determining whether an event is an important medical event. An important medical event may not be immediately life-threatening and/or result in death or hospitalization. However, if it is determined that the event may jeopardize the subject or may require intervention to prevent one of the other AE outcomes, the important medical event should be reported as serious.

Examples of such events are intensive treatment in an emergency room or at home for allergic bronchospasm; blood dyscrasias or convulsions that do not result in hospitalization; or development of drug dependency or drug abuse.

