After lorlatinib treatment for 4 weeks, patients will receive an imaging assess. The patients who achieve PR or SD with oligometastasis (refer to target lesions with residual disease, a maximum of 3 organs, and no more than 5 lesions in total) should continue lorlatinib treatment and will receive imaging assess per 8-12 weeks. If target lesions indicate stable in 2 consecutive imaging, investigators will organize MDT and comprehensively evaluate patients' will to decide and choose local therapy. The local therapy includes surgery, ablation and, radiotherapy et al. After local therapy, patients should continue taking lorlatinib. While those who achieve CR or with multiple metastasis will continue lorlatinib treatment without any local therapy.

To dynamically monitor ctDNA changes in ALK + NSCLC patients during Lorlatinib treatment; to explore the correlation between ctDNA and Lorlatinib treatment efficacy .Patients need check the ctDNA-seq (10000x) in plamsa with NGS at baseline,4weeks after lorlatinib treatment and at disease progression.

Subjects will be on lorlatinib therapy until disease progression or unacceptable toxicity, new systemic anticancer therapy instituted, withdrawal of consent, death, or investigator decision dictated by protocol compliance, whichever occurs first.

Patients received continuous daily PO dosing of lorlatinib 100mg QD with/without locally therapy, from the date of first dosing (per the current protocol) or until one of the following criteria were met (whichever occurred first): disease progression; initiation of a new anti-cancer therapy; unacceptable toxicities; global deterioration of health-related symptoms; pregnancy; withdrawal of consent; loss to follow-up; death; investigator decision dictated by protocol non-compliance; or study termination. Patients who have progressive disease (PD) (per RECIST v1.1, by investigator review) and for whom the investigator believes it is in their best interest to continue lorlatinib treatment are allowed to continue lorlatinib therapy, at the discretion of the investigator, until any alternate or additional systemic anti-cancer therapy regimen was implemented.

At the time of progression and termination of study treatment, the patients could receive

any therapy at the judgment of the investigator. This study will take 1 years to enroll subjects, and each subject will be followed up for survival status and subsequent cancer therapies up to 60 months from the date of first dosing.

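### Section 8.4 gives two incompatible periods for recording a lung-cancer death as a Grade 5 SAE, so sites could count late cancer deaths differently

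*Protocol*

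**What the plan says.** The two rules stand in one paragraph of Protocol 8.4, after the list of seriousness criteria.

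- **Narrow rule (first sentence).** Progression of the malignancy "should not be reported as a SAE unless the outcome is fatal within the safety-reporting period".
- **Wide rule (third sentence).** "If the malignancy has a fatal outcome during the study or within the safety-reporting period, then the event leading to death must be recorded" both as an AE and as a Grade 5 SAE. For detail it points to Section 8.6. Section 8 ends at 8.4 in the table of contents and in the body.

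The periods are set elsewhere.

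- Section 8.1 runs active SAE reporting from consent "through and including 28 calendar days after the last administration of the investigational product".
- Section 3.1 has collection of AEs and SAEs "terminate till 28 (and no more than 35) days after administration of the last dose of lorlatinib".
- After that period, 8.1 still wants other SAEs sent to the company, "unless the SAE is attributed by the investigator to complications of either the underlying malignancy or any subsequent anti-cancer therapy". Section 3.1 says: "After this period, only lorlatinib-related SAEs must be reported to the Pfizer".
- Section 3.1 also says that "each subject will be followed up for survival status and subsequent cancer therapies up to 60 months from the date of first dosing", and plans a 60-month observation period per patient. Section 5.2 keeps patients who stop the drug for toxicity in the trial.

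Section 9.3 summarises adverse events in everyone who took at least one dose, by type, frequency, CTCAE severity, timing and relationship to treatment. It names no time window.

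**The concern.** Take a patient who stops lorlatinib at month 20, moves to another therapy and dies of lung cancer at month 40. Under the narrow rule this death is not an SAE. Under the wide rule it is a mandatory Grade 5 SAE in a study of first-line lorlatinib. The paragraph that should tell the site what to do gives both answers, and the section it cites for help is missing.

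Several sites take part (about 6 in the Introduction, about 8 in 3.1), and each could follow a different sentence in good faith. The Grade 5 line of the safety summary would then mix two definitions. Safety and tolerability are a stated secondary objective, so that line will be read.

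**Working it through.** **Textual check.** Consider a malignancy death after the post-dose window and before month 60.

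| Place | Is it an SAE to record or report? |
|---|---|
| 8.4, first sentence | No |
| 8.4, third sentence | Yes, Grade 5 |
| 8.1, after the active period | No, if attributed to the malignancy or later therapy |
| 3.1, after the window | No, unless related to lorlatinib |

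Three statements agree and one does not. Sections 8.1 and 3.1 differ from each other for other late SAEs, but both leave this death out.

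**Size.** The protocol gives no fatal-SAE count, death rate or OS figure, so there is nothing to reproduce. If p is the share of malignancy deaths that fall inside the window, then

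wide count / narrow count = 1 / p.

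This gives 10 at p = 0.10, 5 at 0.20, 2 at 0.50 and 1.3 at 0.75. To see what p might be, an illustrative simulation was run per 100 patients.

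*Inputs from the Protocol.* PFS on lorlatinib in the cited phase 3 trial (Introduction) is 78%, 68.2% and 63.5% at 12, 24 and 36 months. The window is 28 days after last dose (8.1), or 28/30.44 = 0.92 months. Follow-up is 60 months (3.1). Treatment beyond progression is allowed with no fixed duration (3.1).

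*Assumptions not in the Protocol.* Every PFS event is a progression. Every death is a malignancy death. The month 24 to 36 hazard continues to month 60. Survival after progression is exponential with median m of 3, 6, 12 or 24 months. Lorlatinib continues 0, 3, 6 or 12 months beyond progression, or until death if sooner.

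*Monthly hazards.*
- Months 0 to 12: −ln(0.78)/12 = 0.0207
- Months 12 to 24: −ln(0.682/0.78)/12 = 0.0112
- From month 24: −ln(0.635/0.682)/12 = 0.00595

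PFS at 60 months = 0.635 × exp(−24 × 0.00595) = 0.55, so about 45 of 100 patients progress.

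*Results.* Cells show the narrow count, with the wide/narrow ratio in brackets.

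| Median survival after progression | Wide count | 0 months beyond progression | 3 months | 6 months | 12 months |
|---|---|---|---|---|---|
| 3 months | 43.6 | 8.5 (5.1) | 26.5 (1.6) | 35.3 (1.2) | 41.6 (1.0) |
| 6 months | 41.9 | 4.5 (9.3) | 16.1 (2.6) | 24.2 (1.7) | 33.6 (1.2) |
| 12 months | 37.8 | 2.3 (16.2) | 9.1 (4.2) | 14.4 (2.6) | 22.6 (1.7) |
| 24 months | 29.4 | 1.2 (24.9) | 4.8 (6.2) | 8.0 (3.7) | 13.4 (2.2) |

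*Hand check of the 0-month column.* The share dying within 28 days is 1 − 2^(−0.92/m), which is 0.19, 0.10, 0.052 and 0.026 for the four medians. Times 45, this gives 8.6, 4.5, 2.3 and 1.2, in line with the simulation.

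*28 or 35 days.* With m = 6 and no treatment beyond progression, 35 days (1.15 months) gives 45 × (1 − 2^(−1.15/6)) = 5.6 deaths, against 4.5 at 28 days. The window discrepancy is small beside the main conflict, but it changes the same count.

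**The case against.** **The 60 months is inferred.** Section 8.4 does not define what it means by the study. It could have meant time on treatment, but then the wide limb would add nothing to the safety-reporting period, and no text says so. The 60-month reading has a similar weakness: it makes the second limb almost redundant, because the window nearly always falls inside the 60 months. So the phrase is loosely drafted, not a clear 60-month rule. That stands, and it is also why sites could read it either way.

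**Other sections largely settle it.** Section 8.1 is the section on reporting periods, and with 3.1 it excludes late malignancy deaths. This shows which rule was probably intended. It does not remove a conflicting mandatory instruction from 8.4. Nor does it help to say that 8.4 speaks of recording and 8.1 of reporting, since 8.1 makes the CRF the route by which SAEs are reported.

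**A several-fold inflation.** A reader might infer that the wide rule inflates fatal SAEs 5- to 10-fold. That range is only 1/0.20 to 1/0.10, from an assumed 10 to 20% of deaths inside the window. It leaves out the treatment beyond progression that 3.1 permits, which moves deaths into the window and can bring the ratio close to 1.

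**Drug-related deaths hidden.** A reader might also infer that late cancer deaths would hide deaths due to the drug or to local therapy. Section 9.3 characterises events by timing and relationship as well as severity, so they can be separated. The analysis window may also be set in a statistical analysis plan that is not at hand. That plan could restrict the table, but it could not make the sites' instructions consistent.

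**Conclusion.** The contradiction holds on the text alone and needs no assumption beyond reading the study as the planned observation period. A lung-cancer death after the window is excluded by one sentence of 8.4 and required by another, and the cited section does not exist. The fatal-SAE count behind the 9.3 summary could therefore differ by site.

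The size cannot be fixed from the Protocol. The scenarios give a ratio of about 1 to 25: about 5 to 25 if lorlatinib stops at progression, falling towards 1 if survival after progression is short and most patients stay on the drug until close to death. A several-fold difference is possible but not established.

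OS and TTD do not depend on SAE classification and are unaffected. The study is described as descriptive, with no hypothesis tested. This is an inconsistency in safety reporting that should be corrected, not a threat to the main results.

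**What to change.** Reconcile 8.4 with 8.1 and 3.1 so that one period governs when a malignancy death is recorded as a Grade 5 SAE. Deleting *during the study or* from the third sentence is the smallest edit that agrees with 8.1, 3.1 and the first sentence of 8.4. The choice of reporting rule remains the sponsor's.

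In the same edit:
- state one end of the safety-reporting period in 8.1 and 3.1, since tying the rule to that period otherwise carries over the 28 versus 28-to-35-day difference;
- say that malignancy deaths after that period count as OS events and are not SAEs;
- correct or remove the reference to Section 8.6.

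The cost is a few words in two sections and a note to sites. No new data are needed, because survival status is already collected and OS counts death from any cause. If patients have already been enrolled, malignancy deaths recorded so far should be checked against the rule that is adopted.
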